7.2.2 Evaluation during each study visit during study treatment

PARAMETERS	INVESTIGATIONS	TIMING
1. Clinical Examination	Weight, vital signs, ECOG PS, clinical tumor measurement, and physical examination. Concurrent illness; concomitant medications,	Before study treatment administration. In addition, on days 1, vital signs will be recorded, 1 and 2 hours after administration, in order to capture possible peak effects
2. ECG	ECG	Only on days 1 and 22 : Before study treatment administration, then on day 1 only at 1 and 2 hours after administration , in order to capture possible peak effects
3. Adverse Events*	Adverse events Serious adverse events have to be declared up to 30 days after last OTX015/MK-8628 intake regardless of relationship with study drugs and beyond if drug related.	Before study treatment administration Within 24 working hours
4. Hematology**	CBC with platelets counts, WBC differential and hemoglobin, INR. Bone marrow aspiration for patients with leukemia and myeloma	Before study treatment administration Only on day 1 (if not done at screening) then on days 8 ^{§,} 22 and 43 (for AL). For myeloma, mandatory only to confirm CR), then at the investigator's discretion
	Bone marrow aspiration in all patients	In case of grade 4 thrombocytopenia lasting > 3 days
5. Biochemistry***	LDL, HDL, β2-microglobulin (for patients with myeloma), AP, LDH, CPK, CRP, ASAT, ALAT, total bilirubin, serum creatinine, ionogram (sodium, potassium, chloride, HCO3-), calcium, phosphorus, magnesium, total protein, albumin, glucose. Apo A1	Before study treatment administration Only at day 22 for Apo A1
6. Urinalysis	Dipsticks for albumin, blood and glucose	Before study treatment administration
7. Pharmacokinetics	Plasma sampling. Please, refer to the sampling schedule (section 7.3.3.1).	Only on Days 1,-2 (complete PK) or 1 (limited sampling)- , then days 8, 15 and 22 (all patients)
8. Optional fresh tumor cell sampling for biomarkers and intracellular PK for patients with other hematological malignancies	Biopsy of superficial lesion	Day 1 (or within 14 days prior to first study drug administration) and Day 15 + 7
9. Tumor measurement	CT-scan or MRI in patients with evaluable tumor masses; PET-scan if deemed necessary for proper response assessment	Every 6 -8 weeks
8. Plasma M-component and/or BJ proteinuria	In patients with multiple myeloma	Only on day 1, 22, then every 3 weeks.

Days 1, 8, 15 and 22 of the first 21 days (first cycle), then every 3 weeks

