7.2.4 Follow-up

After the end of therapy visit, subjects will be followed until resolution of TEAEs possibly related to the study treatment or the return to baseline value, if abnormal, or the categorization into sequella.

All deaths occurring within 30 days after the last dose of study treatment (regardless of relationship to study treatment), or considered related to study drug treatment (regardless of their date of occurrence) will be reported as serious adverse events (SAEs). Deaths occurring more than 30 days after the last study medication administration and not related to drug treatment will not be considered as SAEs.

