8.1 ADVERSE EVENT DEFINITIONS (21 CFR§312.32)

• Adverse event (AE) means any untoward medical occurrence associated with use of a drug in humans, whether or not considered drug related. (The term treatment emergent adverse event [TEAE] covers any unfavorable and unintended sign, symptom, syndrome, or illness that develops or worsens during the period of observation in the clinical study). Surgical or other procedures themselves are not TEAEs. The condition for which the surgery/other procedure is required is a TEAE, if it occurs or is detected during the study period. Planned surgical or other procedures planned/permitted by the study protocol and the condition(s) leading to these measures are not TEAEs, if the condition(s) was (were) known before the start of study treatment. In the latter case the condition should be reported as medical history.

- **Suspected adverse reaction (SAR)** means any AE for which there is a reasonable possibility that the drug caused the AE. A "reasonable possibility" means there is evidence to suggest a causal relationship between the drug and the adverse event, such as:
 - A single occurrence of an event that is uncommon and known to be strongly associated with drug exposure (e.g., angioedema, hepatic injury, Stevens-Johnson Syndrome);
 - One or more occurrences of an event that is not commonly associated with drug exposure, but is otherwise uncommon in the population exposed to the drug (e.g., tendon rupture);
 - An aggregate analysis of specific events observed in a clinical trial (such as known consequences of the underlying disease or condition under investigation or other events that commonly occur in the study population independent of drug therapy) that indicates those

events occur more frequently in the drug treatment group than in a concurrent or historical control group.

SAR implies a lesser degree of certainty about causality than adverse reaction, which means any AE caused by a drug.

- Adverse reaction (AR) means an AE caused by the drug.
- Serious adverse event (SAE) or serious suspected adverse reaction (SSAR) is an event that, in the view of either the investigator or sponsor, results in any of the following outcomes:
 - Death occurring within 4 weeks after the last administration study drug, irrespective of cause, or within any interval if related to the study drug
 [Although death may occur as a result of the basic disease process, all deaths occurring

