8.5 PERIOD OF OBSERVATION

For the purposes of this study, the period of observation for collection of AEs extends from the start of treatment with investigational product until the end of study treatment (i.e. 30 days after the last study drug administration), except for adverse events related to study drug, which must be reported during follow-up period until resolution or change of causality from related to non-related or initiation of further antitumor therapy.

If the investigator detects a SAE in a study subject after the end of the period of observation, and considers the event possibly related to prior study treatment, he or she should contact the sponsor to determine how the adverse event should be documented and reported.

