# 6. STATISTICAL METHODOLOGY

# 6.1 GENERAL CONSIDERATIONS

The statistical analysis will be performed by eXYSTAT, under the responsibility of the Sponsor OncoEthix GmbH and the study CRO, OTD, on the basis of the present document.

The statistical analysis will be performed using SAS® software, version 9.4 in a Windows XP operating system environment.

The baseline value is defined as the last available value prior to administration of the investigational product.

The study treatment phase is defined as the period between the date of first administration of investigational product and the date of last administration of investigational product + 30 days.

No replacement of missing values is planned, other than those noted in Section 6.2. Thus the number of patients included in the analyses may vary depending on availability of the parameter considered.

Descriptive statistics will be provided by dose level (DL1 to DL5 or DL6 then expansion cohort, depending on the disease cohort) and overall for each of the two patient cohorts (AL and OHM), and by time point when appropriate, according to the nature of the variable.

- For quantitative variables, descriptive statistics will include: number of missing values, number of observed values, minimum, maximum and median or mean and standard deviation.

- For qualitative variables, descriptive statistics will include: number and percentage of missing values, number of observed values, frequencies and percentages (only for the overall column) per modality.

Calculated statistics and percentages will be displayed with one decimal, unless otherwise specified.

No statistical tests will be performed due to the descriptive nature of this analysis.

In terms of terminology, the mention of "by dose level and overall" will always correspond to the following, according to the cohort:

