# **12. SAFETY EVALUATION**

# **12.1** SAFETY VARIABLES

Safety analyses will be performed in the Safety Population other than for DLT which will be presented in the evaluable for DLT population. All safety data from the study treatment phase will be presented.

Safety data are obtained from clinical and physical examinations, as well as vital signs evaluation.

TEAEs / signs and symptoms of disease observed by the investigator (preferably by the same physician for the same patient) or reported by patients to the study nurses will be recorded and graded according to NCI-CTCAE version 4.03.

Clinically significant laboratory results are those which have clinical consequences. The seriousness, the action taken regarding study medication and patient participation in the study, relation to study medication and the most likely cause, should then be recorded.

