# **12.4 ADVERSE EVENTS**

Adverse events occurring or worsening after the treatment start date and before the last study treatment administration date +30 days were considered treatment-emergent adverse events (TEAEs).

- 21 -

Summary AEs (number and % of patients) will be tabulated by DL and overall for patients with:

- at least one treatment-emergent grade 1-5 adverse event (TEAE)
- at least one related treatment-emergent grade 1-5 adverse event (TEAE)
- at least one treatment-emergent grade 3-5 adverse event (TEAE)
- at least one related treatment-emergent grade 3-5 adverse event (TEAE)
- at least one serious TEAE
- at least one serious TEAE related to the study treatment
- a TEAE leading to treatment discontinuation
- a related TEAE leading to treatment discontinuation
- a TEAE leading to death

Tables of individual TEAEs (number and % of patients) grouped by primary System Organ Class (SOC) and Preferred Term (PT; for MedDRA) will be presented by DL and overall. Patients will be counted only once per primary SOC and PT.

These tables will be presented for all cycles as well as for cycle 1 only.

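### Drug-related SAEs and deaths more than 30 days after the last dose are reportable under the protocol but fall outside the SAP's by-dose-level safety counts

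*SAP*

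**What the plan says.** **Protocol**

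- Section 7.2.2 has SAEs declared "up to 30 days after last OTX015/MK-8628 intake regardless of relationship with study drugs and beyond if drug related". The end-of-therapy table in 7.2.3 repeats the rule.
- Section 7.2.4 covers deaths within 30 days of the last dose from any cause. Beyond that, deaths "considered related to study drug treatment (regardless of their date of occurrence) will be reported as serious adverse events (SAEs"). Section 8.1 says the same of related deaths, whatever the interval.
- Section 8.5 ends AE collection 30 days after the last dose, "except for adverse events related to study drug, which must be reported during follow-up period until resolution", a change of causality, or the start of further antitumor therapy.
- Section 8.1 defines a TEAE by reference to the period of observation and does not itself state a number of days.

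**SAP**

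- Section 6.1 defines the study treatment phase as "the period between the date of first administration of investigational product and the date of last administration of investigational product + 30 days".
- Section 12.1 states: "All safety data from the study treatment phase will be presented".
- Section 12.4 ends the TEAE window at the same point, for related and unrelated events alike: events that start or worsen after treatment start and "before the last study treatment administration date +30 days were considered treatment-emergent adverse events (TEAEs"). Its nine summary rows are all TEAE rows, for example "at least one serious TEAE related to the study treatment", and so are the tables by SOC and preferred term.
- Section 12.5 is a listing of deaths and related SAEs, and its wording refers to the treatment period.
- Section 14 names three changes from the protocol: the per-protocol population, overall survival, and the PK/PD relationship analyses. The safety window is not among them.

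**The concern.** The protocol asks sites to go on reporting related SAEs and deaths after day 30, but the SAP gives those reports no place in its counts. The safety profile is a stated secondary objective. The rows most used to judge tolerability at the recommended dose are the related ones: related grade 3-5 events, related SAEs and fatal events. Leaving events out can only lower these rows.

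Late events are plausible enough to plan for. Protocol 3.2.1 warns that drug-induced liver injury can appear or progress after the drug is stopped. Protocol 8.2 sets out contacts that continue until death. The SAP has also dropped the overall survival analysis, which was another place where late deaths would have been counted.

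**Working it through.** No sample-size, power or alpha figure bears on this point, so there is no plan figure to reproduce. The check is a comparison of text plus simple arithmetic.

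**1. The two windows side by side**

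| Event more than 30 days after the last dose | Protocol | SAP 12.4 counts |
|---|---|---|
| Related SAE | Declared (7.2.2, 7.2.3) | Outside the window |
| Related death | SAE at any time (7.2.4, 8.1) | Outside the window |
| New non-serious related AE | Ambiguous (8.5) | Outside the window |
| Unrelated event | Not collected (8.5) | Outside the window |

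The first two rows are a clear mismatch. The third is not: the 8.5 exception can mean new onsets, or only continued follow-up of events that have already begun. The fourth row agrees.

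**2. Tracing one case**

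Take a related SAE with onset 45 days after the last dose.

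- It is an SAE under protocol 7.2.2.
- Since 45 > 30, it is not a TEAE under SAP 12.4. It enters none of the nine summary rows and none of the SOC and preferred-term tables.
- It can appear in the by-patient AE listing (SAP 12.4.1), which has a field for initial or follow-up phase and a field for emergence.
- If it is a death, it may appear in the 12.5 listing, depending on whether the reference to the treatment period limits deaths as well as SAEs.
- If it is a laboratory abnormality, SAP 12.6.3 may count it, because grades there are taken over the whole study.

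**3. Can such events be observed?**

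The end-of-therapy visit is at 35 ± 5 days after the last dose, that is, days 30 to 40. Of these 11 days, 10 are later than day 30. The visit day is not the onset day, but a related event that starts on days 31 to 40 can be found at this scheduled visit and then be left out of the counts.

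**4. Size per omitted patient**

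The column Ns in SAP 6.1 are:

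- AL: 3+3+4+3+4+8+7+6+7+19+16 = 80
- OHM: 5+3+4+7+6+7+3+5+5+16 = 61
- Total: 80 + 61 = 141, which matches SAP section 7

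One omitted patient lowers a rate by 100/N percentage points:

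| Group | N | 100/N |
|---|---|---|
| All enrolled | 141 | 0.7 |
| AL | 80 | 1.25 |
| OHM | 61 | 1.6 |
| AL expansion, both groups (19+16) | 35 | 2.9 |
| OHM expansion | 16 | 6.3 |

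SAP 6.1 prints percentages only in the overall column. In a dose-level column the effect is therefore one patient missing from a count.

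**The case against.** The strongest reply has five parts.

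- **Section 8.5 may not extend the TEAE window.** Its exception runs until resolution or a change of causality, which suits follow-up of existing events. Its next paragraph deals with possibly related SAEs found after the period has ended, and that paragraph would have little to do if the period were open-ended for related events. This stands. A reader might infer that the protocol's TEAE definition is plainly wider than the SAP's, but the text does not settle it. The point rests instead on the SAE and death rules in 7.2.2, 7.2.3, 7.2.4 and 8.1, which are not ambiguous.
- **Reporting is not tabulation.** The protocol says what must be declared and does not fix a table window. That is true, and a 30-day main window is acceptable. It does not explain why a class of events the protocol singles out has no count anywhere in SAP 12.4.
- **The events are not lost.** A reader might infer that late related toxicity disappears from every table. The documents do not support that. The listings can carry it, laboratory grades run over the study, and the discontinuation table (Appendix 16.1, Table i-4) has a row for related death. The shells for all AEs (part B, Table iii-1) and for SAEs (Table iv-1) state no window. Read with 12.1 and 12.4 they inherit the 30-day limit, but the SAP should say so. A listing still gives no count by dose level.
- **The number may be very small.** Mean half-life in healthy volunteers, on a different formulation, was at most 16.3 hours, so day 30 is about 720/16.3 = 44 half-lives after the last dose. A reader might put a rate on late events, for example 1 to 5% (1.4 to 7.1 of 141), but nothing in the documents supports any such rate.
- **The recommended dose is not at stake through the primary endpoint.** This is correct. DLT is a cycle 1 endpoint, with day 43 confirmation for one haematological criterion in AL.

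**Conclusion.** The concern holds in a limited form. The protocol makes related SAEs reportable beyond 30 days and related deaths SAEs at any date. The SAP's TEAE-based counts of AEs, SAEs and deaths stop at last dose + 30 days with no exception, and SAP 14 does not say so. The direction is certain: the omission can only lower the related-event counts. The size cannot be estimated from the documents. It is 0.7 points per omitted patient over 141, up to 6.3 points in the OHM expansion group, and zero if no such event occurred.

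This rests on one reading: that shells without a stated window follow SAP 12.1 and 12.4. It does not rest on 8.5 extending the TEAE definition. It affects the secondary safety description and leaves DLT untouched.

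A separate and minor wording point concerns protocol 8.1. It lists as an SAE "Death occurring within 4 weeks after the last administration study drug, irrespective of cause", while its own bracketed explanation and section 7.2.4 say 30 days. The two differ by 30 − 28 = 2 days and must be reconciled. The SAP counts are not affected.

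**What to change.** 1. Keep the +30-day TEAE window for the main tables.
2. Add to SAP 12.4 and 12.5 a count by dose level, and a listing, of related AEs, SAEs and deaths with onset after last dose + 30 days, flagged as late.
3. For non-serious related AEs, apply the protocol 8.5 limit, so that collection stops when further antitumor therapy starts. Otherwise events arising under the next treatment would be counted.
4. Include related SAEs and deaths at any time, with any intervening antitumor therapy flagged.
5. State the window in the all-AE and SAE shells (Appendix 16.1, part B, Tables iii-1 and iv-1), and make clear in 12.5 whether the treatment period limits the deaths as well as the SAEs.
6. Record the choice in SAP 14.
7. Reconcile the 4 weeks and the 30 days in protocol 8.1 and 7.2.4.

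The cost is one extra table, one listing and a short derivation. Related-event counts may rise slightly. The protocol already requires sites to report related SAEs and deaths, so no new collection should be needed. However, 8.5 leaves the documentation of late SAEs to contact with the sponsor, so the sponsor should check that these reports are in the analysis database.

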# 12.4.1 Listing of Adverse Events by Patient

AEs will be individually described per subject number, presenting: first/last application, treatment phase (Initial or Follow-up), emergence, description, SOC, preferred term, start and end date, duration, the toxicity grade, the relationship to study drug, the action taken and the seriousness.

# 12.5 DEATHS, OTHER SERIOUS ADVERSE EVENTS, AND OTHER SIGNIFICANT ADVERSE EVENTS

All deaths and all SAEs experienced during the treatment period related to the study drug will be separately listed per subject number, presenting: first/last application, treatment phase (initial or follow-up), emergence, description, SOC, preferred term, start and end date, duration, the toxicity grade, the relationship to study drug, the action taken and the seriousness.

# **12.6** CLINICAL LABORATORY EVALUATION

All laboratory values recorded during the study (plus the calculated creatinine clearance) will be individually listed and flagged for values outside reference ranges.

# 12.6.1 Laboratory values over time

Each hematology and chemistry parameter will be described for each visit and by DL.

# **12.6.2** Individual patient changes

A listing of patients with worsening hematology or biochemistry parameters on study will be provided (baseline grade, worst grade, % decrease).

For thrombocytopenia, description of nadir (duration) and recovery (time to recovery) will be provided. A listing of patients experiencing thrombocytopenia during the study will be provided.

# 12.6.3 Individual clinically significant abnormalities

For each hematology and chemistry parameter, number and percentage of patients with at least one clinically significant value (according to the investigator) during the study as well as number and percentage of patients with at least one NCI-CTCAE worst grade of 3 to 5 during the study will be presented by DL.

### 12.7 VITAL SIGNS, PHYSICAL FINDINGS AND OTHER OBSERVATIONS RELATED TO SAFETY

# 12.7.1 Vital Signs

Raw values and changes from baseline of systolic/diastolic blood pressure (mmHg), Heart rate (beats/min) and respiratory rate (/min) will be described for each visit and for the last value during the study treatment phase by DL.

For weight (kg), systolic/diastolic blood pressure (mmHg) and heart rate (beats/min), number and percentage of patients with at least one predefined change (PC)/clinically significant change (CSC) during the study treatment phase will be presented by DL.

Parameter	Predefined change (from baseline)	Clinically significant change
Weight	Increase $\geq 5\%$	
	Decrease $\geq 5\%$	
Systolic blood pressure	Increase $\geq 20 \text{ mmHg}$	≥180 mmHg and PC Increase
	Decrease $\geq 20 \text{ mmHg}$	$\leq$ 90 mmHg and PC Decrease
Diastolic blood pressure	Increase $\geq 15 \text{ mmHg}$	≥105 mmHg and PC Increase
	Decrease $\geq$ 15 mmHg	$\leq$ 50 mmHg and PC Decrease
Heart rate	Increase $\geq 15$ bpm	≥120 bpm and PC Increase
	Decrease $\geq$ 15 bpm	$\leq$ 50 bpm and PC Decrease

Predefined changes and clinically significant changes are defined below:

# 12.7.2 ECG and LVEF evaluations

Absolute and relative differences between max post dosing Day 1 and pre-dosing will be presented by DL and overall. Absolute and relative difference between end of study value and pre-dosing will be presented by DL and overall.

# 12.7.3 Physical examination

Physical examination will be individually listed.

# **13. PK ANALYSES**

The PK analyses will performed by the Laboratoire de Pharmacology [PD] Institut Curie (Hôpital René Huguenin), [name].

A separate PK report will be provided.

# **14. CHANGES FROM PROTOCOL**

The protocol allowed for analysis in a per protocol population (section 11.2). This analysis was not performed as it is not appropriate for a phase 1 study with small expansion cohorts.

Overall survival analysis planned in the protocol (section 7.2.2.7) were not performed.

The secondary objectives allowing for assessment of PK/safety, PD/safety and PK/PD relationships were not performed due to insufficient PD data, while PK analyses were not considered pertinent.

# **15. INDIVIDUAL LISTINGS**

All relevant CRF data will be provided using individual data listings.

All listings will include center number, cohort, patient number, dose level.

